PRIMARY HYPOTHESIS	
Our study has four main hypotheses, each of which will be tested by a different intervention:
 
1) According to government data, programs aimed for women with children are often undersubscribed, which may be largely explained by the fact that many poor women are not aware of the existence of these programs, their potential eligibility, or how to navigate the system to get enrolled. In fact, among the relatively few mothers that do get enrolled, they are often enrolled too late into (or even after) their pregnancy, missing critical windows for fetal development. Given this, we hypothesis that providing information on government programs and enrolment support will improve program take-up and women and children’s outcomes.2) While knowledge on the signature importance of the “fetal origins” and early childhood periods (Barker, 1990, Almond and Currie 2011) is widespread among clinicians and social scientists, the full range of effects may be less known to disadvantaged groups such as women in remote areas in low- and middle-income countries. Thus, to the extent that expectant mothers’ beliefs underestimate the returns of prenatal investments on children’s future outcomes, or misperceive the malleability of fetal health, we hypothesise that interventions that target maternal beliefs starting in early in pregnancy will be effective at promoting children’s future potentials.3) Research has shown that while psychological interventions conferred substantial benefit to mothers, they have not been effective in improving outcomes for children (Baranov et al. 2020, Angelucci and Bennett 2021). A likely cause is that interventions typically start too late (in the third trimester of pregnancy), and we hypothesis that a early start of psychological interventions will result in substantial benefits to mothers’ and children’s outcomes.

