4. AIMS / OBJECTIVES / HYPOTHESES

Our goal is to address three types of adversities that hinder women’s empowerment and early child development in low- and middle-income countries: low take-up of healthcare and other social safety net programs (including cash- and food-transfers), lack of knowledge about the importance of the early years on future child development and long-run outcomes, and psychological constraints associated with maternal depression. We aim to test to what extent these three interventions offer practical opportunities to improve maternal health, birth, and child development outcomes in cost-effective ways. We believe that these interventions might be even more effective than previous similar interventions because we will be targeting women

early in pregnancy (and in some cases even prior to conception), which is considerably earlier than most previous studies aimed at improving maternal and child outcomes.

Our specific **objectives** are:

- 1) Explore what are pregnant women’s views about the idea of a “healthy pregnancy” and how these perceptions translate to actual health behaviours and investments in children.
- 2) Investigate if providing the three following targeted interventions to women early in pregnancy offers cost-effective ways to enhance maternal wellbeing and children’s physical and mental development:
 - a. Information about women’s eligibility to health services and other safety net programs and assist them with the enrolment process.
 - b. Information to pregnant mothers and their families on the importance of the early-life environment, and especially the 9-month in utero period, in laying the foundations for a child’s lifelong success.
 - c. Psychological counselling to pregnant women starting early in pregnancy.

Our study has four main **hypotheses**, each of which will be tested by a different intervention:

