6. RESEARCH PLAN / STUDY DESIGN

Our study is comprised of three treatments. In treatment 1, project officers employed by the research team, who will be located in study area, will provide information over the phone to each treated household on their eligibility (yes or no) of government's cash and food transfer programs, as well as where and how to enrol, and assistance with enrolment for eligible mothers.

Treatment 2 involves providing information to pregnant mothers and their families on the importance of the early-life environment, and especially the 9-month in utero period, in laying the foundations for a child's lifelong success. Eligible and willing participants who would be randomly assigned to receive this treatment will be contacted by our project officers, and the officer will provide the following information over the phone:

“A healthy pregnancy, wherein mothers take care of themselves and their children during their pregnancy, is extremely important for their children health and economic outcomes. Starting from as early as the 9th week of pregnancy, mothers who eat nutritious food and think positively give birth to healthier children who grow up to be healthier adults. A healthy diet during pregnancy such as this one, (this is based on study conducted in a similar setting, see: <https://bmjopen.bmj.com/content/bmjopen/7/8/e015393.full.pdf>)

Meal	Food	Quantity (one dish=250mL)
Breakfast	Rice	1.5 dishes
	or	
	Chapati (medium size)	3 pieces
	Vegetables	1 dish
	Egg	1
Mid-morning snack	Lentil (thick)	1 dish
	or	
Lunch	Seasonal fruit(s)	1 piece/dish
	Milk product(s)	1 dish
Afternoon snack	Rice	3 dishes
	Lentil (thick)	1 dish
	Leafy/non-leafy vegetables	1.5 dishes
	Meat/fish/egg	1 piece
Dinner	Milk	1 glass
	Seasonal fruit(s)	1 piece/dish
	Puffed rice with molasses or Biscuits	1 dish
Dinner	Rice	2 dishes
	Lentil (thick)	1 dish
	Leafy/non-leafy vegetables	1.5 dishes
	Meat/fish/egg	1 piece
	Milk or Curd	1 glass / 0.5 dish

	উপাদান	পরিমাণ
সকালের নাস্তা	ভাত	১½ বাটি (২৫০ মি.লি.+১২৫ মি.লি.)
	অথবা	অথবা
	অটার কুটি	৩টি (মাঝারি)
	সবজি ভাজি	১ বাটি (২৫০ মি.লি.)
	ডিম ভাজি	১টি
মাঝারি নাস্তা (সকাল ১০-১১)	যে কোন মৌসুমি ফল (মেম্বন-কলা/আম/কঁচালা/পেয়ারা/পেঁপে ইত্যাদি)	১টি (মাঝারি)
	অথবা	অথবা
দুপুরের খাবার	ভাত	৩ বাটি (২৫০ মি.লি.+২৫০ মি.লি.+২৫০ মি.লি.)
	মন ডাল	১ বাটি (২৫০ মি.লি.)
	শাক-সবজি	১ বাটি (২৫০ মি.লি.)
	মাছ/মাংস/ডিম	১ টুকরা (মাঝারি)
বিকালের নাস্তা	মুগ	১ গ্রাস
	অথবা	অথবা
সন্ধ্যার খাবার	দুধের তৈরী পায়েস/ফিরনি/পিঠা	½ বাটি (১২৫ মি.লি.)

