To evaluate the impact of these three interventions, we will conduct a 3x2 factorial RCT across two sub-districts in rural Bangladesh. The two information treatments will be cross randomized with the one mental health intervention. The mental health intervention will be randomized at the Union Health and Family Welfare Centre (UHFWC) level (there are 20 total UHFWCs across the 2 Upazilas), stratified by sub-district, and allocated at a 1:1 ratio. We will then randomly select 120 villages within subdistricts, stratified by UHFWC, to participate. The information interventions will be randomized at the village level, stratified by UHFWC, with 40 villages receiving information and enrolment support for government programs, 40 villages receiving additional information on the importance of early life conditions, and 40 control (no information) villages. Eligible participants will be pregnant women and mothers with young children aged 6 months or younger. We will aim to recruit 22 women per village to be part of the study sample.

We will use two types of data, (i) the data from the digital information system of Kapsasia Model built at the sub-district level by the local government, which we call *administrative data*, and (ii) household and individual survey data including elicitation of maternal beliefs of prospective and existing mothers that we will collect as a part of the study, which we call *household survey data*. This survey will be conducted on the sample of 22 women per village for a **total sample of 2,640 women**. The administrative data include information (e.g., age, education, occupation, mobile phone number, pregnancy status, birth outcomes, number of children) on *all* registered newly married couples in our study area, including the 22 women per village in our study sample, and will identify key outcomes such as pregnancy status and birth outcomes. We will conduct a baseline survey with an endline 10 months later, and we plan to conduct a midline survey by phone (which will likely be funded using internal funds² from the University of Sydney and University of Melbourne) to measure parental inputs in the in utero period. The schedule of enrolment, intervention and evaluations is given in Figure 1.

² They have not been mentioned in the budget as no firm commitment has been received yet.

The study schedule	Study period													
	Baseline							Midline				Endline		

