	1st month	2nd month	3rd month	4th month	5th month	6th month	7th month	8th month	9th month	10th month	11th month	12th month	13th month	14th month
Enrolment														
Eligibility Screening	X													
Consent collections		X												
Randomization & allocation to treatments and control group			X											
Interventions/ Treatments														
1. Information and enrolment support to govt. programs				X	X	X	X	X	X	X	X			
2. 1 + Information on the importance of early life conditions				X	X	X	X	X	X	X	X			
3. Psychological counselling				X	X	X	X	X	X	X	X			
Evaluations														
Compliance Check - if individuals and groups assigned to treatments and controls are in fact complying to the assignment					X	X	X	X	X	X	X			
Household characteristics and other basic information, houses, lands, and asset ownership, economic activities and employment, beliefs, women mental health, preferences		X										X		
Parents time and monetary investment on children								X						
Anthropometry & health, children’s mental health and development, take up of health care services, participation in social transfers/safety net programs, parenting style, parents time and monetary investment on children, food intake/share, food insecurity & non-food expenditures, women empowerment, intimate partner violence													X	
Data Analysis														X X
Report Writing/ Publication														X X

Figure – 1: Schedule of enrolment, intervention, and evaluations

Power Calculation: Given the sample sizes above and accounting for the varied clustered design, we would be powered to detect a Minimum Detectable Effect (MDE) size of 0.31 of a standard deviation (SD) change for the mental health intervention (randomized at the Health Centre (UHFWC) level with the conservative estimate of 20 centers). For the information arms, we would be powered to detect a 0.19SD change for either of the information interventions (main effects only). As benchmark for the MDEs on mental health interventions, Rahman et al. (2008) found that a mental health intervention similar to the one proposed here improved mothers’ mental health by 0.70SD, while Sikander et al. (2019) found that a more scalable, peer-delivered version of the intervention increased mothers’ mental health by 0.30SD. A tele-counseling intervention in Bangladesh improved mental health by 0.65SD (Vlassopolous et al. (2021)).

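### The second information arm is programme support plus early-life information, so the design gives the add-on effect of the early-life message but not its stand-alone effect or its complementarity with transfers, both of which the wording promises

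*Protocol*

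**What the plan says.** **Allocation.** Section 6 of the Protocol states that "we will conduct a 3x2 factorial RCT across two sub-districts in rural Bangladesh". The information factor has three village-level groups: "40 villages receiving information and enrolment support for government programs", then "40 villages receiving additional information on the importance of early life conditions, and 40 control (no information) villages". The participant-numbers row of the Synopsis gives the same split. The schedule in Figure 1 lists the second information treatment as "2. 1 + Information on the importance of early life conditions".

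**Description of the treatments.** Earlier in section 6, "Treatment 2 involves providing information to pregnant mothers and their families on the importance of the early-life environment", with no mention of programme support. The intervention list in the Synopsis and objective 2 in section 4 also set out the three interventions as separate items. The opening of the Synopsis says they will be studied singly or together.

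**Hypotheses.** The Synopsis says "Our study has four main hypotheses, each of which will be tested by a different intervention", and section 4 repeats it. Hypothesis 2 concerns interventions that act on maternal beliefs and sets no condition about programme support. Hypothesis 4 holds that information, economic transfers and counselling reinforce one another. Section 3 says the study will test whether the three are complements.

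**Power.** Section 6 says "we would be powered to detect a 0.19SD change for either of the information interventions (main effects only"). It does not say which two groups are compared.

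**The concern.** By Figure 1, the six cells are (control, programme support, programme support plus early-life message) crossed with (counselling, no counselling). The early-life message never appears without programme support. Two stated aims do not fit this layout.

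First, the effect of the early-life message on its own cannot be estimated without assuming that it does not interact with programme support. Hypothesis 4 predicts the opposite.

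Second, complementarity between the early-life message and the transfers that programme support opens up needs a message-only cell, and there is none.

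The text also leaves room for misattribution. Calling arm 2 simply the early-life treatment and giving one detectable effect for main effects invites a comparison of each information arm with control. For arm 2 that comparison includes everything programme support achieves, and hypothesis 1 expects programme support to improve outcomes for women and children. A gain from cash or food enrolment could then be reported as a gain from changed beliefs.

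**Working it through.** **1. What the cells identify.** Within one level of counselling, let the mean outcome be m0 in control villages, m1 in arm 1 and m12 in arm 2. Let a be the effect of programme support alone, b the effect of the early-life message alone, and c their interaction.

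- Arm 1 − control: m1 − m0 = a
- Arm 2 − arm 1: m12 − m1 = b + c
- Arm 2 − control: m12 − m0 = a + b + c

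The third line is the sum of the first two, so there are two independent contrasts for three unknowns. The add-on effect b + c is identified. Neither b nor c is identified separately, and c is the complementarity of early-life information with programme support. Because the information factor is crossed with counselling, the difference in a between counselling levels, and the difference in b + c, are both estimable.

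**2. The stated detectable effect.** Inputs from the Protocol: 40 villages per information group, 22 women per village, so 40 × 22 = 880 women per group (and 120 × 22 = 2,640 in total, as stated). The power paragraph gives no significance level, power or ICC. Assumed here: two-sided 0.05, 80% power, ICC varied.

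Formula: detectable effect = (1.960 + 0.842) × √[DE × (1/880 + 1/880)], with DE = 1 + 21 × ICC.

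| Assumed ICC | DE | Standard error | Detectable effect |
|---|---|---|---|
| 0.01 | 1.21 | 0.0524 | 0.147 SD |
| 0.05 | 2.05 | 0.0683 | 0.191 SD |
| 0.10 | 3.10 | 0.0839 | 0.235 SD |

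Solving for the stated 0.19: DE = (0.19 / 2.802)² × 440 = 2.02, so ICC = (2.02 − 1)/21 ≈ 0.049. The figure is therefore consistent with a comparison of 40 with 40 villages, but it cannot be confirmed from stated inputs. Arm 1 versus control, arm 2 versus control and arm 2 versus arm 1 are all 40 versus 40, so the same value applies to each. It does not show which contrast was meant.

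**3. What arm 2 versus control would show if the message did nothing.** Set the added effect b + c to 0 and give programme support a true effect a. The probability of a significant result is Φ(a/SE − 1.96) + Φ(−a/SE − 1.96). The Protocol gives no expected value for a, so a range is shown.

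| True effect of programme support | ICC 0.01 | ICC 0.05 | ICC 0.10 |
|---|---|---|---|
| 0.05 SD | 16% | 11% | 9% |
| 0.10 SD | 48% | 31% | 22% |
| 0.19 SD | 95% | 80% | 62% |
| 0.30 SD | over 99% | 99% | 95% |

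Example at ICC 0.05 and a = 0.10: 0.10/0.0683 = 1.46; Φ(−0.50) ≈ 0.31, and the other tail is negligible. The 80% at 0.19 SD is no independent result: it restates the assumed power at the detectable effect. In all these scenarios arm 2 versus arm 1 stays at 5%.

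**4. What a stand-alone arm would cost.** Splitting the 120 villages into four groups of 30, at ICC 0.05, gives a pairwise detectable effect of 2.802 × √[2.05 × 2/660] = 0.221 SD, against 0.191 SD now.

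**The case against.** - **An add-on design is legitimate, and hypothesis 2 can be tested in it.** This stands. Arm 2 versus arm 1 is a randomised comparison, stratified by health centre, with the same detectable effect. Hypothesis 2 does not say that the message works without programme support. The absence of a message-only arm limits what the result means; it does not bias that comparison.
- **The contrasts may be set in the statistical analysis plan.** This also stands. A reader might infer that the trial will test hypothesis 2 as arm 2 versus control and so credit the message with the effect of programme support. The Protocol nowhere says so, the 0.19 SD fits either contrast, and the analysis plan is not at hand. The percentages above are conditional on that choice.
- **The factorial label is correct.** Agreed. Three information levels by two counselling levels is a 3x2 factorial, and the Protocol does not claim a full factorial in three interventions. A reader might also infer that hypothesis 4 as a whole cannot be tested. That goes too far, because the interactions of both information arms with counselling are identified.
- **The treatment description gives content and the allocation gives arms, so the two can be read together.** Only in part. Someone working from the treatment description would give the 40 villages (880 women) the message alone; someone working from Figure 1 would give them both components. Taken alone, the word additional in the allocation sentence could mean merely further information, but then Figure 1 would be wrong.

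What survives is the conflict between the cumulative arm and the promise of individual effects, and a complementarity claim that no analysis plan can rescue.

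**Conclusion.** The point holds in a limited form. On Figure 1 and the allocation wording, early-life information is given only on top of programme support. The Protocol therefore states two properties that its design lacks: an individual effect for each intervention, and a test of complementarity between early-life information and transfers. Both follow from the allocation and need no numerical assumption.

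The possible misattribution is conditional. Should hypothesis 2 be judged by arm 2 versus control, an inert message would be declared effective about 11% to 99% of the time for programme-support effects of 0.05 to 0.30 SD. That rests on an assumed two-sided 0.05 and ICC of 0.05, and on a range of effects that the Protocol does not supply. Severity: should be fixed. The randomisation is sound, and a valid contrast is available at the stated detectable effect.

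**What to change.** 1. **Reconcile the arm descriptions.** Bring the Synopsis (opening paragraph, hypotheses, intervention list), the objectives and hypotheses in section 4, and the treatment 2 text in section 6 into line with Figure 1. The sponsor should confirm that the 40 villages of arm 2 receive both components; the steps below take Figure 1 as it stands.
2. **Name the contrasts.** Hypothesis 1: arm 1 versus control. Hypothesis 2: arm 2 versus arm 1, described as the effect of adding early-life information where programme support is in place. Arm 2 versus control: the effect of the package, attributed to neither component. In the power paragraph, say which contrasts the 0.19 SD refers to.
3. **Narrow the complementarity claim.** In hypothesis 4 (Synopsis and section 4) and in section 3, limit it to the interaction of the information arms with counselling, and drop the claim to test complementarity between early-life information and transfers.

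The cost is wording only: allocation, sample and detectable effect do not change. The price is that the conclusion on hypothesis 2 becomes conditional on programme support. If the sponsor wants the stand-alone effect, it needs its own arm before the allocation planned for month 3, at the loss of precision shown in step 4 of the working.

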
POPULATION
	
Our population includes newly married women, pregnant women, and mothers with young children aged 6 months or younger located in two subdistricts of Gazipur district in Bangladesh. According to the Demography and Health Surveys of 2014, women in Bangladesh tend to marry early. By age 18, 50% are married and their first child arrives 1.5 years later, which means that many women become mothers as teens. Moreover, 98.6% get married and nearly all have at least one child. As a result, there is virtually no selection into fertility in this setting. Two thirds of women deliver their child at home, have between one and two antenatal visits. Half have primary education or less, and less than 35% work outside home (half of which are employed in agriculture). Husbands are on average 10 years older, have similar levels of education, and the vast majority work in agriculture or in the informal sector. Moreover, Bangladesh has one of the highest rates of malnutrition in the world. 20% of children born in the country every year are born either “small” or “very small” (Demography and Health Survey, DHS 2014), 41% of those below the age of 5 are stunted, and about five million children are out of school (World Bank, 2015).

SELECTION AND ENROLMENT
	
Eligibility criteria for inclusion:
 
 1. Listed in the digital database of Kapasia Model 2. Permanent residence of any of the two subdistricts of Gazipur district in Bangladesh 3. Newly married women 4. Pregnant women 5. Mothers with young children aged 6 months or younger 
To be eligible, women must fulfill the first and the second criteria, any of the criteria from 3 to 5 must be fulfilled.

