11. TIMELINES / MILESTONES

An approximate study timeline is provided in Figure 2. We plan to complete the study within 14 months from start. In the first month, the eligibility criteria of participants which will be selected from the Kapasia Model digital database, will be re-checked, and informed consents of the eligible participants will be sought. This will be followed by commencement of the baseline survey in the second month of the study, and the random allocation of participants to different treatments will be achieved in the third month. The list of participants that will receive psychological counselling will be given to the relevant implementing partner Moner Bondu,

and the rest of interventions will be carried out by the research team. In the fifth month, compliance to treatments and control status will be checked followed by a midline telephone survey in the eighth month. We will conduct the endline survey after 10 months of the intervention followed by data analysis and report writing / manuscript preparation.

[figure not shown]

Figure 2: Study Timeline

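### The midline call meant to measure in utero inputs is one wave in study month 8, when most women enrolled at any stage of pregnancy would already have delivered

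*Protocol*

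**What the plan says.** Section 6 plans a midline survey by phone "to measure parental inputs in the in utero period". Section 11 checks eligibility at the outset ("In the first month, the eligibility criteria of participants"), places the "commencement of the baseline survey in the second month of the study", and has the compliance check "followed by a midline telephone survey in the eighth month". Figure 1 agrees on month 8 and starts all three interventions in month 4. The only measurement row that Figure 1 marks in month 8 reads "Parents time and monetary investment on children", with no prenatal item named.

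On who is enrolled, Section 6 states: "Eligible participants will be pregnant women and mothers with young children aged 6 months or younger". The Synopsis also lists newly married women and requires that "any of the criteria from 3 to 5 must be fulfilled". Neither text limits gestation. Section 4 speaks of reaching women early in pregnancy, sometimes before conception, but as an expectation about the interventions and not as an entry criterion.

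The midline is to be paid from university funds, on which a footnote in Section 6 says: "They have not been mentioned in the budget as no firm commitment has been received yet".

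**The concern.** The call has a purpose tied to pregnancy and a date tied to the study calendar. With enrolment open at any gestation, the two coincide only for women who were very early in pregnancy when they joined. Mothers already post-partum at enrolment have no pregnancy that the interventions could have affected, unless they conceive again.

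Prenatal behaviour is what the early-life information message asks mothers to change. If most answers come after delivery, they are recalled over intervals that differ between women, and each woman answers knowing how the birth went. No other wave is described as measuring prenatal inputs, so there is no second chance to collect them concurrently.

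**Working it through.** **Inputs from the protocol.** Eligibility check in month 1, baseline in month 2, interventions from month 4, midline in month 8 (Section 11, Figure 1). In utero period of 9 months (Section 6). Sample 120 × 22 = 2,640, which matches the stated total. The protocol gives no figure for the share still pregnant at midline, so there is none to reproduce.

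**Assumption.** Gestation at enrolment is not given. I take it as uniform from *lo* to 9 months, with *lo* between 0 and 2.

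**Step 1: women pregnant at enrolment.** Share still pregnant = max(0, (9 − gap) − lo) / (9 − lo). The gap is 6 months from baseline or 7 from the eligibility check; 5 is the shortest gap tried.

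| Gap | lo = 0 | lo = 1 | lo = 2 | Delivered by the call |
|---|---|---|---|---|
| 5 | 4/9 = 44% | 3/8 = 38% | 2/7 = 29% | 56-71% |
| 6 | 3/9 = 33% | 2/8 = 25% | 1/7 = 14% | 67-86% |
| 7 | 2/9 = 22% | 1/8 = 12% | 0/7 = 0% | 78-100% |

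**Step 2: women whose pregnancy reaches month 4.** These are the women in whom prenatal inputs could respond to the interventions. With lo = 1:
- From baseline (2 months to the intervention start, 6 to the call): 6/8 are still pregnant in month 4 and 2/8 in month 8, so 2/6 = 33%.
- From the eligibility check (3 and 7 months): 5/8 and 1/8, so 1/5 = 20%.

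The remaining 67-80% delivered between months 4 and 8. Their recall therefore reaches back at most 8 − 4 = 4 months to the birth.

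**Step 3: share of the whole sample under the Section 6 eligibility text.** Assuming a steady flow of births, pregnant women and mothers of infants stand as (9 − lo) : 6.
- Gap 6, lo = 0: 9/15 × 3/9 = 20%, or 528 women.
- Gap 6, lo = 1: 8/14 × 2/8 = 14%, or 377 women.
- Gap 6, lo = 2: 7/13 × 1/7 = 8%, or 203 women.
- Across gaps of 5 to 7 months: 0% to 27%, or 0 to 704 women.

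**Step 4: adding newly married women (Synopsis).** Suppose a fraction w of 10-33% of the sample, conceiving at h = 3-10% a month (both assumed), with gap 6 and lo = 1 for the others. Ongoing pregnancies = w(1 − e^(−6h)) + (1 − w) × 0.143, which gives about 15-24% of the sample (383 to 646 women).

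**Step 5: early recruitment.** With a 6-month gap, gestation uniform on 1-3 months leaves 100% still pregnant, 1-4 months 67%, and 0-6 months 50%. With a 7-month gap, 1-3 months leaves 50% and 1-4 months 33%.

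**The case against.** The strongest reply is that Section 6 does not require a woman to be pregnant when she is called. A recently delivered mother can describe her whole pregnancy, and for women exposed in pregnancy the birth lies at most about four months back. Women who delivered before month 4 had no exposed prenatal period, so no timing of the call could show an effect in them. This stands: the data need not be lost, and the recall is bounded. But the protocol does not say that recall is intended or for whom, and recall after a known birth outcome is weaker than a concurrent report.

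A second reply is that the trial aims to reach women early. That is a fair reading of intent, and Step 5 shows that it could resolve the problem. No eligibility rule enforces it, however, and admitting mothers of infants points the other way.

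Third, Section 11 calls its timeline approximate. A shift of a month does not change the result: even a 5-month gap leaves 56-71% delivered.

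Fourth, mothers told what a healthy pregnancy looks like may over-report it while pregnant too. That is correct; changing the timing removes only the recall and the knowledge of the birth outcome.

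A reader might infer that a primary outcome rests on a call without firm funding. The protocol does not support this. Section 9 lists parental investment as primary without naming prenatal investment, and Figure 1 schedules time and monetary investment again at endline. Maternal beliefs, which hypothesis 2 targets, are measured in months 2 and 12. The funding position is openly disclosed.

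**Conclusion.** The mismatch is real. With recruitment at any gestation, as the eligibility text allows, about 67-86% (six-month gap) to 78-100% (seven-month gap) of women pregnant at enrolment have delivered by the midline call. Among those pregnant when the interventions start, about 20-33% are still pregnant. These figures rest on gestation being uniform up to nine months, which the protocol neither states nor rules out; they fail if enrolment is in fact concentrated in early pregnancy.

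A reader might take the 14% in Step 3 as a ceiling on the share of the sample still pregnant. It is one case in a range: 8-20% at a six-month gap, 0-27% across five to seven months, and 15-24% when newly married women are added under the stated assumptions. Ongoing pregnancies remain a minority in all of these. The consequence is a weaker, partly retrospective measure of prenatal inputs. It does not amount to the loss of a listed primary outcome.

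**What to change.** Before baseline:

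- Record gestation at the baseline interview, or take it from the administrative data if held there. Section 6 gives pregnancy status as an example of that data's content but mentions neither gestation nor due date.
- Trigger the same single call by gestation, after the month-4 intervention start and before expected delivery.
- Ask and analyse prenatal items only for women whose pregnancy overlaps the intervention period. Include those who conceive later if newly married women are enrolled.
- Reconcile the purpose in Section 6, the month-8 row of Figure 1, which names only investment in children, and the timeline in Section 11. Settle whether newly married women are eligible, since Section 6 and the Synopsis differ.

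The cost is one baseline question and calls spread over several months, with no calls added. Two limits remain. Women late in pregnancy at enrolment will have had little exposure before their call, and over-reporting by informed mothers is not removed.
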